Utilizing All Health System Contacts to Offer Postpartum Family Planning (PPFP) to Pregnant Women and Women within Twelve Months Postpartum in Ethiopia

Study Protocol

Jhpiego

Unique Protocol ID: IRB00007143

February 2, 2018

JHSPH IRB Research Plan for New Data Collection

PI Name: [name]
Study Title: Utilizing All Health System Contacts to Offer Postpartum Family Planning (PPFP) to Pregnant Women and Women within Twelve Months Postpartum in Ethiopia
IRB No: IRB00007143
PI Version No./Date: V3_February 2, 2018

I. Aims of the Study: Describe the aims/objectives of the research and/or the project's research questions or hypotheses.

The objectives and sub-objectives of this study are to:

- 1) Assess the effect of contacts that women/couples have with the health system (from the *kebele* [sub-district] level to the health facility level and back), into which postpartum family planning (PPFP) messages are systematically integrated, on uptake of PPFP through 12 months postpartum in Ethiopia. These health contacts span several levels: at health facilities from trained health professionals, and at community settings from Health Extension Workers (HEWs) and Health Development Army (HDA), a cadre of community volunteers.
 - a. Assess the extent and type of existing contacts that women/couples have with the health system during pregnancy, birth, and in the postpartum period and the degree to which they receive PPFP messages during these health contacts.
 - b. Assess the relationship between frequency and type of contact to uptake of PPFP and recommended child feeding and immunization practices (estimate the dose-response effect of each additional health contact).
- 2) Estimate the added effect of a community-based intervention (i.e. beyond the health center) to promote PPFP messaging at antenatal and postpartum contact points by community health workers (HEWs, HDA) on uptake of postpartum family planning through twelve months postpartum in two clusters of health center and health posts, as compared to health center-only PPFP counseling and services in two comparison clusters.
 - a. Measure "baseline" PPFP uptake through recall of women with prior birth history and their PPFP use after those recall births (sub-sample of women with prior birth history)
 - b. Prospectively assess uptake of PPFP among postpartum women by type of health contact, timing postpartum, and contraceptive method

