The Ethiopian health system envisages that a number of health contacts should occur for women and babies from pregnancy through to the extended postpartum. Figure 1 below illustrates these contacts.

Figure 1: Possible Contacts with the Health System for Pregnant Women in Ethiopia

Month	4	5	6	7	8	9		1	2	3	4	5	6
Client	Pregnancy						Birth	Postpartum Period					
HDA	x	x	x	x	x	X	Home	X	x	x	x	x	x
HEW	Quarterly visits: 2-3 times during last two trimesters of pregnancy							Quarterly visits: 2-3 times during first 12 months postpartum					
HC	ANC1 Before end of 4 th month		ANC2 24-28 weeks	ANC3 32 weeks	ANC4 36 weeks	Facility		PNC w/in 48 hours; w/in 6 weeks					
								DPT1 6 weeks		DPT2 10-14 weeks		DPT3 14-22 weeks	

About 84% infants receive at least one dose and more than 60% receive two doses of basic vaccines. A substantial number of mothers also seek care for their child's fever, diarrhea and other illness from health providers. This study will take these contact occasions as opportunities for promoting PFP, but also to reinforce the need to fully vaccinate children.

III. Study Design

- A. Provide an overview of your study design and methods. The study design must relate to your stated aims/objectives. Details will be requested later. If your study also involves analysis of existing data, please complete Section XI, "Secondary Data Analysis of Existing Data" in the last part of this research plan. If your study ONLY involves analysis of existing data, please use the research plan template for secondary data analysis (JHSPH IRB Research Plan for Secondary Data Analysis of Existing Data/Specimens).

This implementation research will use a quasi-experimental mixed method design with two arms. The intervention arm will have integrated PFP messages at each level of health system contacts. The control arm will continue to deliver the existing FP services at primary health care centers only.

The primary study population is a cohort of pregnant women, enrolled between the 2nd and 3rd trimester of pregnancy in both arms, who will be followed to twelve months post-partum. We will interview the women at study enrollment and at the end of the study. We will track women's contacts with the health system, particularly regarding PFP counseling, decision making and contraceptive adoption, through chart reviews of routinely collected facility and community based health records and registers (e.g. family folders that may be modified for study).

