Health providers (at Health Center)	Mixed methods questionnaire (going through each point of service – ANC, delivery, PNC and immunization)	
 • Integration of PFPF messages in ANC • Delivery of contraceptive methods at birth, including PPIUD, or in postnatal contacts • Experience with scheduling mobile services or referrals for permanent methods • Barriers to PFPF counseling and service delivery, including stock outs, organization of services, manpower, confidence to deliver, etc. • Experience with record keeping and analysis of PFPF data
District (woreda) health managers	Key Informant Interviews	
 • Attitudes towards PFPF integration; • Barriers/Facilitators • Experience with data reviews, analysis of data to address gaps • Experience addressing management or systems issues with FP service delivery
Pregnant and postpartum Women	Census of all pregnant women in the catchment area Questionnaire for all women 6-9 months pregnant F/U and re-interview all women 1 year later Review Integrated MCH/Family Health Card	
 • Attitudes and use of FP – past use, current use (once delivered) • Family support for FP, spouse, MIL, FIL (ask who are most influential) • Attitudes on immunization, facility delivery, plans for delivery, infant feeding, care seeking for self or sick baby • # of health contacts, # of ANC visits, place of delivery, PNC visits at facility or home, immunization visits, BF practices, return to fertility, timing of adoption of FP if adopted, rationale for not, what was most influential for those who did adopt (and didn't)

Study Population	Data Collection Method	Type of Information/Data Collected
		
 Perception of risk of pregnancy and motivation to avoid another pregnancy Experience with woman held card, if brought with them to all contacts with the system; was it helpful? Ability to communicate method choice without card
Registers, Referrals at Health Center, Health post level	(Revised longitudinal register)	Ability to track pregnant women's PFP counselling, decision making on method choice and uptake of PFP # of women in register, completeness of register Follow up mechanism

The Table 2 provides details on the general study timeline, program activities and study related activities.

Timeline	Program Activities	Research-related Tasks
Preparatory phase (1 st 4-6 months)	Woreda level engagement of stakeholders	

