	Assessment of sampled health facilities readiness	Identification of data collectors
	Development and pretesting of SBCC and training materials for HEWs including how HEWs will train HDA (in adjoining woreda to avoid contamination)	Pre-testing of translated questionnaires for pregnant women and household members
	Development and pre-testing of HEW and HC M&E Tools	Abstraction tools for health records, development of monthly site monitoring visit documentation tool
	PPFP Counseling Training (2 day course, with more people)	Training of data collectors
	PPIUD/Implant Training (5 day course for subset)	
	Training of HEWs in PPFP counseling and promotion of PPFP messages at community level, assessment and refresher in implant skills	
Baseline		
 Census of pregnant women, enrollment of study participants (research team member paired with HDA team leader), Interviews of study participants and household members

Timeline	Program Activities	Research-related Tasks
Intervention implementation run time (15 months)	
 • HEWs train HDA team leaders and team leaders train HDA • Ongoing household visits by HDA and HEW and promotion of PFP at community level • Ongoing monthly meetings between HEWs and HDA team leaders – review of data on pregnant and recently delivered women • Post training follow up of PFP/trained health providers and HEWs 	Study Monitoring: 
 • Monthly F/U of HC records, tracking of births and PFP uptake among postpartum women using selected health facilities • Record review and abstraction of HEW data • Documentation of PFP, PNC or immunization service delivery issues
Endline (after 15 months)		
 • Follow up interviews with enrolled women • Interviews of HCW, HEW, • Focus Groups with HDA • In depth interviews of Woreda stakeholders
Analysis and report writing (4 months)		Data analysis Report Writing Journal Writing
Dissemination		Dissemination workshop in Ethiopia

B. Provide a sample size and a justification as to how you arrived at that number. If you use screening procedures to arrive at a final sample a table may be helpful.

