This study will be implemented 2 primary health care units (PHCUs), comprised of one health center and all kebeles/health posts in their catchment area, in Hitosa Woreda and 2 PHCUs in Lude-Hitosa Woreda. We randomly assigned 1 PHCU in each Woreda to the intervention and control arms. So out of 4 PHCUs in each Woreda, 1 was selected for intervention and 1 for control.

We obtained the total population for each PHCU. To estimate the number of women age 15-49 and expected pregnancies at the time of study survey, we used results from the Ethiopia mini DHS 2014: 43.6% of female residents of selected households were age 15-49 and 7.3% of women age 15-49 were currently pregnant at the time of the Mini DHS 2014.

Table 3: Estimation of eligible population

Arm	Total population	Female population (50%)	Expected females age 15-49 (43.6% of female pop)	Expected current pregnancies (7.3% of women 15-49)	Women 6-9 months pregnant (pregnancies / 3)
Intervention	72,138	36,069	15,726	1148	382
Comparison	52,508	26,254	11,446	835	278

For pregnant women, we calculated the minimum sample size requirements for this quasi-experimental design for the main outcome of interests (adoption of LAM and other modern method by 12-month PP) using the formula:

$$n' = \frac{\{z_{1-\alpha/2}\sqrt{2\bar{p}(1-\bar{p})} + z_{1-\beta}\sqrt{p_1(1-p_1) + p_2(1-p_2)}\}^2 (1 + (m-1)\rho)}{(p_1 - p_2)^2}$$

where, $p = (p_1 + p_2) / 2$

Where p_1 and p_2 are the proportions of women adopting LAM or other modern method in the intervention and control arms, respectively, and Z's are the critical value of the normal distribution at $\alpha=0.05$ and $\beta=0.20$; $1+(m-1)\rho$ captures the design-effect due to cluster based sampling of areas, where m = average size of the clusters and ρ =intra-cluster correlation. We consider a design-effect (deff) of 1.5 for adjusting higher intra-cluster correlation in the observations in the quasi-experimental design.

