Similarly, for focus group discussions with HDA, a waiver of signed informed consent allows for better protection of confidentiality as no identifiers will be collected, including signatures. Many of the HDAs have low or no literacy. The FGD will be recorded for ease in transcription and translation of the discussion, but any names or nicknames will be removed from the transcripts. FGDs will be audio recorded; recordings will be kept in a locked cabinet or room and will be destroyed after the study is complete and the file is closed.

2. Identify the countries where the research will take place, and the languages that will be used for the consent process.

Country	Consent Document(s) (adult consent, parental permission, youth assent, etc.)	Languages
Ethiopia	Consent	Amharic, Afan Oromo

C. Study Implementation:

See Table 5 for information on study implementation

Table 5: Study implementation procedures					
Study Population	Main Data Collection Method	Other Study Procedures	Number of contacts	Duration of Research Interview (Only)	Place of Interview
Health Extension Workers	Post intervention Questionnaire (covering each point of service – ANC, delivery, PNC & immunization)?	Orientation to study Training on PPFP counseling and promotion of PPFP to HDA Training on health records tools Monthly follow up	~19: Pre study training and start up (~3); monthly during study (15 months); Endline (1)	60 minutes	Health Post
Health providers (at Health Center)	Post intervention Questionnaire (covering each point of service – ANC, delivery, PNC & immunization)	Orientation to study Training on PPFP counseling Training on PPIUD and implants (subset of providers) Training on health records tools (and analysis?) Monthly follow up	~19: Pre study training and start up (~3); monthly during study (15 months); Endline (1)	60 minutes	Health Center
Health Development Army (HDA)/HDA team leaders	Post intervention Focus Group Discussions	Existing HEW/HDA contacts utilized for study activities.	1: FGDs	120 minutes	Health Post
District (woreda) health managers	Post intervention Key Informant Interviews	Orientation to study Ad hoc debrief on study monitoring	~6	45 minutes	Woreda Health Office
Pregnant and Postpartum Women	Pre-intervention questionnaire for all women 6-9 months pregnant Post intervention F/U questionnaire 6-9 months postpartum		2	Pre-Interview: 60 Post-Interview: 60	Household

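### Protocol Table 5 puts the women's only postpartum interview at 6-9 months, against the 12-month interview and 12-month primary outcome stated elsewhere; the cell needs correcting

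*Protocol*

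**What the plan says.** The outcome and the follow-up are described in 12-month terms in most places:

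- Protocol section I (Aims) looks at the effect of contacts "on uptake of PPFP through 12 months postpartum in Ethiopia".
- Protocol III.A describes a cohort "who will be followed to twelve months post-partum", interviewed at enrolment and at the end of the study.
- Protocol III.B bases the sample size on "adoption of LAM and other modern method by 12-month PP" and says women are interviewed at enrolment and at 12 months postpartum.
- Protocol V.B (Consent Process) says the second interview is about a year postpartum.
- Protocol Table 2 gives "Intervention implementation run time (15 months" and places the women's follow-up interviews at "Endline (after 15 months".
- SAP section A defines the primary outcome among interviewed women as use of a modern method in the 12 months after birth.

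Two tables read differently. Table 5 (Protocol V.C) gives pregnant and postpartum women two contacts, one interview before and one after the intervention, and the latter is the "Post intervention F/U questionnaire 6-9 months postpartum". In the same table, the rows for health workers give contacts "monthly during study (15 months); Endline (1", so the study period there is 15 months with endline after it. Table 1 (Protocol III.A) says "F/U and re-interview all women 1 year later" without saying whether the year runs from enrolment or from delivery.

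**The concern.** A 12-month outcome can be ascertained in full only by an interview at or after 12 months. Table 5 allows one postpartum interview and puts it 3-6 months too early, with no later contact to recover uptake in the remaining months. The table also disagrees with itself: an interview at 6-9 months postpartum is not post-intervention if the intervention runs for 15 months.

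Table 5 is where a field team would look for the schedule. If the cell were followed, first use of a method after the interview would be missed in both arms. The measured proportion would be uptake by 6-9 months, a different quantity from the one in the SAP and the one that was powered.

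Other data would not fill the gap as the plan stands. The monthly health-center follow-up in Table 2 covers women who use the selected facilities, and SAP section C uses facility service statistics to triangulate what women report, not to replace it.

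**Working it through.** **1. Timing implied by each statement.** With a 9-month pregnancy assumed, months postpartum at interview = months since enrolment − (9 − month of pregnancy at enrolment).

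| Source | Timing stated | Months postpartum |
|---|---|---|
| Table 5 | 6-9 months postpartum | 6-9 |
| III.A, III.B, V.B | 12 months or about a year postpartum | about 12 |
| Table 2 | 15 months after baseline | 15 − 3 = 12 (enrolled month 6) to 15 − 0 = 15 (enrolled month 9) |
| Table 1, counted from delivery | 1 year | 12 |
| Table 1, counted from enrolment | 1 year | 12 − 3 = 9 to 12 − 0 = 12 |

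Under Table 5 the unobserved part of the window is 12 − 9 = 3 months to 12 − 6 = 6 months.

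**2. The plan's own sample size.** Inputs from Protocol III.B: 20% vs 10%, α = 0.05 two-sided, power 80%, design effect 1.5. The protocol's formula gives

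n = 1.5 × {1.960·√(2 × 0.15 × 0.85) + 0.842·√(0.2 × 0.8 + 0.1 × 0.9)}² / 0.10² = 1.5 × 198.96 = 298.4, so 299 per arm, as stated.

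Allowing for 20% loss, 299/0.8 = 373.75, against the 375 stated. The figure reproduces, and it belongs to a 12-month outcome.

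**3. Illustration if the Table 5 cell were followed.** The documents give no month-by-month uptake, so a curve has to be assumed:

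p(t) = 1 − (1 − p₁₂)^((t/12)^k), with p₁₂ = 10% and 20%, and the same Weibull shape k in both arms.

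Power at 299 per arm = Φ{[(p₁ − p₂)·√(299/1.5) − 1.960·√(2p̄(1 − p̄))] / √(p₁(1 − p₁) + p₂(1 − p₂))}.

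Check at 12 months: (1.412 − 0.990)/0.500 = 0.844, power 80.1%.

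| Interview | Early-weighted, k = 0.5 | Constant hazard, k = 1 |
|---|---|---|
| At 6 months | 7.2% vs 14.6%, power 66% | 5.1% vs 10.6%, power 52% |
| At 9 months | 8.7% vs 17.6%, power 75% | 7.6% vs 15.4%, power 69% |
| Spread evenly over 6-9 months | 8.0% vs 16.1%, power 71% | 6.4% vs 13.0%, power 61% |
| Per arm for 80% power, spread evenly | about 373 | about 466 |

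For the evenly spread case the proportions are p(t) averaged over 6 to 9 months. In both scenarios the absolute difference shrinks (from 10 points to about 8.2 and 6.6), and that is what costs power.

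**The case against.** The strongest reply is that this is one stray cell. The words 6-9 months appear just above it for the stage of pregnancy at the first interview, and the second use looks like an echo. Nothing outside the cell puts the interview at 6-9 months postpartum, while the aims, design overview, sample size, consent section, Table 2 and SAP all point to 12 months or later. That stands. A reader might infer that the study was designed around a 6-9 month interview, or that it is underpowered. The documents do not support either: under the schedule stated elsewhere, few or no women are interviewed early and the 299 per arm holds.

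The second reply concerns size. A reader might assume late-weighted uptake and obtain a much larger loss (k = 2 gives 43% power with interviews spread over 6-9 months). The documents lean the other way. Most postpartum contacts in Figure 1 fall early (postnatal care within 48 hours and 6 weeks, vaccination from 6 to 22 weeks), the analysis plan in V.C groups uptake timing by delivery, postnatal care and immunization, and the sample-size outcome includes LAM. Health extension worker visits do run over the full 12 months, so late uptake is not excluded, but the late-weighted figure should not be relied on.

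Third, a reader might conclude that the SAP must confine the primary logistic model to women interviewed at or after 12 completed months. That does not follow. It would exclude a woman seen slightly before 12 months, which complies with the consent section's approximate timing, and it would narrow the SAP's denominator of interviewed women. SAP section A already plans life-table and hazards analyses, which can accommodate unequal follow-up, and mentions imputation and non-response weighting.

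**Conclusion.** The contradiction is real, lies in current text and concerns the timing of the interview that yields the primary outcome. Table 5 as written cannot deliver that outcome and should be corrected. It is most likely a drafting slip, so the finding is an inconsistency to remove, not evidence that the design or sample size is wrong.

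The 3-6 month gap follows directly from the stated timings. The fall in power from 80% to about 71% or 61% is an illustration. It applies only if the cell is followed, and it rests on assumed uptake curves with the same shape in both arms and on interviews spread evenly over 6-9 months. The figures are not bounds. Table 1 is a lesser ambiguity: it agrees with 12 months if the year is counted from delivery, and falls short for most women if counted from enrolment.

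**What to change.** In Table 5, replace the timing of the women's follow-up questionnaire with an interview at 12 months postpartum, timed from each woman's delivery date and not held before the 12-month window closes. In Table 1, say that the one-year re-interview is counted from delivery. Both changes bring the tables into line with Protocol III.A, III.B and V.B. No restriction of the primary logistic model is needed; the few women who may be reached early can be handled by the hazards analyses and missing-data options already in SAP section A.

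The cost is two table edits and no additional interviews. There is a small scheduling consequence. A woman enrolled at month 6 of pregnancy reaches 12 months postpartum exactly at month 15, with no slack. Protocol III.A also describes enrolment between the second and third trimester, and a woman enrolled at month 5 would be only 15 − 4 = 11 months postpartum at month 15. Any such woman would need a slightly later interview.

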We require a minimum of 299 women in postpartum observation period in each arm to detect an increase of at least 10% contraceptive prevalence rate (CPR) in the intervention arm, compared to the women in the control arm (20% vs 10% in the intervention and control arm, respectively) with $deff=1.5$ at 80% statistical power. Assuming about 20% lost-to-follow-up and non-response rate, we target to enroll 375 women in each arm. We consider that it will be sufficient to select 1 PHCU and its attached *kebeles* in each of the two *woredas* to ensure adequate sample size, with 2 PHCU randomly assigned to the intervention area (1 per *woreda*) and 2 to the control area (1 per *woreda*). The eligible women in 3rd trimester who consent to participate in the study voluntarily will be recruited and be interviewed at enrollment and at 12-month PP.

We used $p_1=0.2$ (20% PP contraceptive uptake by the final round of observation in the intervention arm) and $p_2=0.1$ (10% in the comparison arm). We considered $deff=(1+[m-1]\rho)= 1.5$. Because we are targeting 375 sample size of pregnant women in each arm consisting of 2 PHCUs, this implies $m=188$ AND $\rho=0.0027$.

Because the selected PHCUs are adjoining *woredas* of the same zone, it is expected that they will be quite similar, and in addition, the underlying population are all similar in terms of postpartum status; hence ρ very small (the larger the heterogeneity, the larger the ρ value). The Ethiopia DHS 2011 results suggest that the $deff$ of contraceptive use in all 11 regions are much smaller than the national level $deff$ of CPR (Appendix B – Estimates of Sampling Errors); *woreda* level $deff$ is expected to be much smaller due to less heterogeneity at *woreda* level, compared to the region/state level. In all regions, method specific $deff$ was <1.5 . So, we considered that of $deff=1.5$ is applied in this study is reasonable and practical. A study on postpartum use of contraceptive method at a *woreda* level in Ethiopia also had $deff=1.5$ (Abera Y, Mengesha ZB, Tessema GA. Postpartum contraceptive use in Gondar town, Northwest Ethiopia: a community based cross-sectional study. BMC Women's Health. 2015;15:19.)

Sample size requirements are included below based on the average number of providers and HDAs and managers in each *kebele*. See Table 4: Sample Size Summary

Table 4: Sample Size Summary

Study Participant	Intervention (2 PHCU)	Comparison (2 PHCU)	Total
Pregnant women	375	375	750

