Study Population	Main Data Collection Method	Other Study Procedures	Number of contacts	Duration of Research Interview (Only)	Place of Interview
	Review Client held Integrated MCH/Family Health Card (post intervention)				
Registers, Referrals at Health Center, Health post level	(Revised longitudinal register) For HEW monitoring tool: Ease of use, helpful for data review meetings, etc		12: monthly data review and abstraction	N/A	Health Post and Health Center

4. Provide a brief data analysis plan and a description of variables to be derived.

After data have been thoroughly examined for quality, the study team will perform exploratory data analysis of the key variables for checking frequency distributions, measures of variability, central tendency, and data outliers. We will also check for incomplete data and undertake an imputation strategy, if needed.

We will examine the differences in contraceptive use behavior by study arms for the following outcomes:

- Baseline only: % with past use of postpartum family planning among women with non-first pregnancies
- % of postpartum women who choose a method prior to delivery (by # of ANC contacts)
- % uptake of FP by PP timing (Delivery, PNC, immunization) and type of method
- % of ANC and PNC contacts where FP was discussed or provided (by type of contact, i.e., HDA, HEW, HCW, other)
- Duration of exclusive breastfeeding/Introduction of complementary foods
- % initiated LAM and the duration of LAM use
- % of women received counseling during immunization
- Immunization coverage of infants of enrolled women by month postpartum (doses of DPT1, 2 and 3 and drop out rates)

We will perform both “intent to analysis” to examine the net differences between the two study arms, adjusted for confounding covariates, and “per-protocol analysis” to examine “dose-effect” of health system contacts. We will fit multivariable logistic regression models for examining the differences in binary outcome variables (e.g., method selection during ANC; FP discussions during contacts, etc). We will use hazards regression model for examining the duration (discontinuation) of LAM use in first 6-month PP and for analyzing the uptake of modern contraceptive method by timing since delivery.

1. Describe whether you are collecting or storing personal identifiers, and if yes, why you need them, and when and how you plan to dispose of them. Signatures on consent forms are considered to be identifiers.

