#### A. Quantitative interviews with Women:

After data have been thoroughly examined for quality, the study team will perform exploratory data analysis of key variables such as checking frequency distributions, measures of variability, central tendency, and data outliers. We will also check for incomplete data and consider strategies to handle missing values such as undertaking an imputation strategy and weighting adjustments for non-responses.

We will compare differences by study arm for key variables. Analysis will account for clustering of variables at kebele (village) level using the Taylor linearization method. Differences between the arms for categorical variables will be assessed using the Pearson chi-squared test with the Rao-Scott correction. Differences in continuous variables will be assessed using an adjusted t-test. In case of substantial differences between the study arms, we will perform propensity score matching and perform the analysis with inverse probability weights.

Key descriptive variables:

- Sociodemographic data such as age, marital status, education, and socioeconomic status (nationally representative SES will be determined using the EquityTool described here: <http://www.equitytool.org/>)
- (Baseline only) Proportion of pregnant women with non-first pregnancies (non-primiparous) who previously used family planning
- Number of health system contacts where FP was discussed or provided, by type of contact (ANC, PNC, immunization, etc) and provider (facility provider, HEW, volunteer)
- Proportion of postpartum women who chose a method prior to delivery, by method, and received chosen method
- Proportion of postpartum women who used FP during the first 12 months after giving birth, by method
- Reasons for starting and stopping contraceptive methods and duration of use

- Initiation and duration of exclusive breastfeeding and lactational amenorrhea (LAM); average/median duration of postpartum amenorrhea, PP sexual initiation/PP abstinence
- Partner communication about family planning

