We will fit multivariable logistic regression models for the primary and secondary binary outcomes (see below) to examine differences between the study arms, adjusted for confounding covariates and clustering at kebele level. We will also conduct a “per-protocol analysis” by examining the “dose-effect” of health system contacts on the primary and secondary outcomes, regardless of study arm. We will run two dose-effect models, looking at the association between the outcomes and 1) the total number of contacts and 2) the number of contacts during which FP was discussed as reported by the woman. For the secondary outcome, we will only include contacts during pregnancy since contacts after the birth would not have a temporal effect on whether the woman chose a method prior to delivery.

- Primary outcome:
  - Proportion of interviewed postpartum women who used a modern family planning method within 12 months after giving birth
- Secondary outcome:
  - Proportion of interviewed postpartum women who chose a method prior to delivery

We will also conduct time-to-event analyses using life-table method and use a log-rank test to test for differences in survival distributions between the study arms in terms of the timing of FP uptake after birth. We will perform multivariable hazards model (Cox’s proportional model or parametric model with Weibull distribution in case of non-normality in hazards function) for adjusting confounding covariates and clustering effects.

Additionally, we will run hazards regression models for women who initiated exclusive breastfeeding/LAM after birth to test for differences between arms in the duration of exclusive breastfeeding/LAM use.

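### The baseline measure of postpartum family planning in the Protocol analysis plan and in the SAP does not match the quantity that Objective 2a asks for

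*Protocol*

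**What the plan says.** Three places describe the baseline measure.

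- **Protocol Section I, Objective 2a.** The baseline is to be "uptake through recall of women with prior birth history and their PPFP use after those recall births", and the group is identified as a "sub-sample of women with prior birth history". Both the population and the event are tied to an earlier birth.
- **Protocol Section V.C, item 4 (data analysis plan).** The outcome list has "Baseline only: % with past use of postpartum family planning among women with non-first pregnancies". The numerator is still postpartum use, but the population is now defined by an earlier pregnancy.
- **SAP Section A.** Under "Key descriptive variables" the item becomes "Proportion of pregnant women with non-first pregnancies (non-primiparous) who previously used family planning". The population is again defined by pregnancy, with a gloss about parity, and the numerator is no longer limited to the postpartum period.

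For comparison, the SAP's primary outcome is "Proportion of interviewed postpartum women who used a modern family planning method within 12 months after giving birth". Every woman in that denominator has given birth, and the window is stated.

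**The concern.** Pregnancy and birth are different events. A woman whose earlier pregnancies all ended in loss or abortion is pregnant for a second or later time but has no earlier postpartum period. She belongs in the denominator of the Protocol's analysis item and of the SAP item, and she is outside the group named in Objective 2a. Followed as written, neither analysis text produces the quantity that the objective asks for, and the two do not produce the same quantity as each other.

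The stake is modest. Women are enrolled while pregnant, so recalled use after earlier births is the only level of the outcome before the intervention that the plan describes for them. Objective 2 sets this baseline (2a) next to prospective uptake (2b), so readers are likely to look at the two together. That reading is sound only if both figures refer to women who have given birth and to use after a birth.

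**Working it through.** **Is there a stated figure to reproduce?** The documents give no value for the baseline percentage, nor for the share of women with an earlier pregnancy but no earlier birth. The nearest derived figure is the sample size in Protocol Section III.B, checked here only to see whether the baseline measure feeds it.

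- Inputs: "20% vs 10% in the intervention and control arm, respectively", two-sided α = 0.05, power 80%, design effect 1.5, about 20% loss.
- n = {1.960·√(2·0.15·0.85) + 0.842·√(0.2·0.8 + 0.1·0.9)}² / 0.10² = 198.96.
- 198.96 × 1.5 = 298.4, rounded up to 299, which matches the Protocol.
- 299 / 0.8 = 373.75, rounded up to 374, against the stated target of 375.

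The figure reproduces, and the recalled baseline is not an input.

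**The three definitions side by side**

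| Source | Denominator | Numerator |
|---|---|---|
| Protocol, Objective 2a | Women with an earlier birth | Use after the recalled births |
| Protocol, V.C item 4 | Women with an earlier pregnancy | Past postpartum use |
| SAP, Section A | Women with an earlier pregnancy, glossed as non-primiparous | Any previous family planning use |

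**Effect of the Protocol V.C wording.** Let t be the true percentage among women with an earlier birth (the Objective 2a quantity). Let s be the share of women in the denominator who have no earlier birth. If those women are scored as non-users:

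reported % = t × (1 − s), so the relative understatement is s.

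Both t and s are assumed. The values 10% and 20% for t are borrowed from the design rates only to give a scale.

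| Assumed s | t = 10% | t = 20% |
|---|---|---|
| 1% | 9.9% | 19.8% |
| 2% | 9.8% | 19.6% |
| 5% | 9.5% | 19.0% |
| 10% | 9.0% | 18.0% |
| 15% | 8.5% | 17.0% |

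The absolute shift is 0.1 to 1.5 points at t = 10%, and 0.2 to 3.0 points at t = 20%.

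**Effect of the SAP wording.** Let e be the further share of women with an earlier birth who used family planning only outside the postpartum period. Take women with no earlier birth as never-users, which is the assumption most favourable to a low figure:

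reported % = (t + e) × (1 − s).

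- t = 10%, s = 5%: e = 2%, 5% or 10% gives 11.4%, 14.25% or 19.0%, all above the true 10%.
- t = 20%, s = 10%, e = 2%: 0.22 × 0.90 = 19.8%, just below the true 20%.
- The two effects cancel at e = t·s/(1 − s). For t = 10% and s = 5% this is 0.10 × 0.05 / 0.95 = 0.0053, about 0.5 points. Above that, the SAP figure overstates the Objective 2a quantity.

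The direction under the SAP wording is therefore not fixed.

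**The case against.** The strongest reply is that the Protocol's item is shorthand for Objective 2a. The analysis section calls itself brief, the objective already names the sub-sample, and a woman with no recalled birth might simply be skipped or coded as not applicable. The questionnaire and its skip rules are not in the documents, so this cannot be ruled out. It stands to this extent: the documents do not say that such women are scored as non-users, and the understatement depends on a literal reading of the item. It does not remove the mismatch, because no text provides the not-applicable code, and the SAP's numerator differs in any case.

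A second reply is that nothing formal rests on this item. That also stands. The SAP lists it as descriptive, and no before-and-after or difference-in-differences test against the recalled baseline is specified. Both arms share one definition, so a comparison of this item between arms is distorted only if its ingredients, such as s, differ by arm. The SAP does allow propensity methods if the arms differ substantially, but it does not name this item as the trigger.

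The SAP's gloss may be loose wording for women who are not first-time mothers, which would be close to the objective. A reader might infer from a strict definition of primiparity that women with exactly one earlier birth are dropped, and that a large part of the baseline sample is lost. The documents do not support that: such a woman plainly has a pregnancy that is not her first, so the phrase being glossed includes her. The gloss is ambiguous, and no more than that.

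**Conclusion.** The mismatch is real and minor. Neither analysis text yields the Objective 2a quantity as written.

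- **Protocol V.C item 4:** if women with no earlier birth are scored as non-users, the baseline is understated by a relative amount s. The value of s is unknown; an assumed 5% turns a true 10% into 9.5%.
- **SAP Section A:** the figure is not a postpartum measure and may be higher or lower than the intended one, depending on s and on use outside the postpartum period, neither of which is given.

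A reader might infer that the trial's baseline is known to be too low and that the later gain will therefore be exaggerated. The documents do not support that. The direction can reverse under the SAP, the scoring of women with no earlier birth is not stated, and no planned analysis computes a gain from this baseline. The sample size and the primary arm comparison do not depend on this item.

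**What to change.** Use one definition in Protocol Section V.C item 4 and SAP Section A, aligned with Objective 2a:

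- **Denominator:** women with at least one previous birth. This replaces both the wording based on earlier pregnancies and the parity gloss.
- **Numerator:** women who used family planning postpartum after a recalled birth, preferably within 12 months, to match the primary outcome's window.
- **Coding:** women with no previous birth are excluded as not applicable, and their number is reported.

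The text should also say how a woman with several earlier births is counted, since the objective refers to births in the plural.

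The cost is a few words in each document and a slightly smaller denominator. Objective 2a already requires the birth history. Whether the recall questions capture the timing needed for a 12-month window cannot be checked from the documents. If they do not, the window actually captured should be stated.
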